5.4 Duration of Therapy

In the absence of treatment delays due to adverse event(s), treatment will be planned for 4 weeks followed by 1 week for observation of acute toxicity and 6-months from the completion of WBRT for delayed toxicity or until one of the following criteria applies:

- Disease progression,
- Intercurrent illness that prevents further administration of treatment,
- Unacceptable adverse event(s),
- Patient decides to withdraw from the study, or
- General or specific changes in the patient's condition render the patient unacceptable for further treatment in the judgment of the investigator.

5.5 Duration of Follow Up

Patients will be evaluated for up to two years from the study registration or until death, whichever occurs first. From the date of completion of WBRT, follow-ups would be done through clinic visits every 2 months (\pm 1 week) for the first 6 months, every 3-4 months (\pm 2 weeks) for the next 6 months and every 6 months (\pm 3 weeks) for the next one year. After the first DLT assessment visit (primary endpoint), these visits in the first 6 months can be performed at an outside institution if appropriate research staff (credentialed and registered as a study team member) is available to complete adverse event and neurocognitive evaluation. After the first 6 months of follow up, clinic visits may be replaced by phone calls or visits at an outside institution, if not felt feasible for logistic reasons. Follow up notes or documentation of phone calls must be included in the study chart. Patients removed from study for unacceptable adverse event(s) will be followed until resolution or stabilization of the adverse event.

Follow-up MRI at 6 months (\pm 2 weeks) from the completion of WBRT is required to assess intracranial treatment response and disease control. As guided by institutional practices, MRIs are also recommended to be performed during follow-up visits every 2 months (\pm 1 week) for the first 6 months and every 3-4 months (\pm 2 weeks) for the next 6 months from the completion of WBRT.

5.6 Criteria for Removal from Study

Patients will go off study when any of the criteria listed in Section 5.4 applies. The reason for study removal and the date the patient was removed must be documented in the Case Report Form.

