- e. On Days 15 and 22 of the 28-day dosing schedule, blood will be obtained just prior to the po drug administration and then at 30, 60, 120 and 240 minutes following po dosing. A five minute positive or negative margin on each of the above times on Day 1 (30 through 240 minutes) is acceptable.
- f. %IUDR-DNA cellular incorporation. Sample collection will be prior to study (Day 1) and at Days 8, 15, 22 and 29 of the 28-day treatment followed by first two-month follow up.
- g. Follow-up MRI at 6 months (\pm 2 week) from the completion of WBRT is required. As guided by institutional practices, MRIs are also recommended during follow-up visits every 2 months (\pm 1 week) for the first 6 months and every 3-4 months (\pm 2 weeks) for the next 6 months from the completion of WBRT. If progressive disease is seen on MRI, subsequent evaluations are not required for study.
- h. For patients accrued to part 2 of the study, please send anonymized pre- and post-treatment (up to 6 months from the date of completion of WBRT) scans via FTP or hard copy CD to the study PI for central review of response.
- i. From the date of completion of WBRT, follow-up visits to be done every 2 months (\pm 1 week) for the first 6 months, then and are recommended every 3-4 months (\pm 2 weeks) for the next 6 months then every 6 months (\pm 3 weeks) for the next one year. These visits can be performed at an outside institution if appropriate research staff (credentialed and registered as a study team member prior to the evaluations) is available to complete adverse event, neurocognitive testing and QOL evaluation. After the first 6 months of follow up, clinic visits may be replaced by phone calls or visits at an outside institution. Follow up notes or documentation of phone calls must be included in the study chart.
- j. Neurocognitive and quality of life evaluation to be performed at the D35 assessment time-point and then during follow-up visits every 2 months (\pm 1 week) for the first 6 months from the date of completion of WBRT (for patients without intracranial progression). A total of 5 neurocognitive and quality of life evaluations will be performed: Baseline, D35, 2-, 4- and 6- months from the date of completion of WBRT.
- k. To be performed only if feasible if the patient is removed from the study.
- l. Perform biopsy only if patient has an easily accessible tumor.
- R. Research.

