11.1.6 Intracranial Progression-Free Survival

The date at which intracranial progression is radiographically identified will be used to calculate the intracranial PFS. Intracranial PFS will be measured from the date of start of treatment to time of progression or death, whichever occurs first. Intracranial PFS will be assessed 2, 4, 6 and 8 months after the initiation of study therapy. If intracranial progressive disease is seen on MRI, any subsequent MRI scans will be performed as clinically indicated standard of care.

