13.4.4 Intracranial progression free survival (icPFS) and Overall Survival (OS)

These will be explored using the Kaplan-Meier method. For estimation of icPFS, patients alive without intracranial progression at last follow-up will be censored at the date of the last radiologic assessment whereas intracranial progression or death will be scored as events. The icPFS estimates at 6 months with their standard error of the estimate will be reported. For calculation of OS, patients alive at last follow-up will be censored.

13.4.5 Incidence of delayed neurological toxicity at 2, 4 and 6-months (\pm 1 week) post-completion of WBRT (for patients without intracranial progression) including:

- a. Delayed-recall through HVLT-R**
- b. Quality of life as measured by the FACT-BR**

REFERENCES

1. Posner, J.B. and N.L. Chernik, Intracranial metastases from systemic cancer. *Adv Neurol*, 1978. 19: p. 579-92.
2. Stewart, B.W., P. Kleihues, and I.A.f.R.o. Cancer, *World cancer report*. Vol. 57. 2003: IARC press Lyon.
3. Gaspar, L.E., et al., Validation of the RTOG recursive partitioning analysis (RPA) classification for brain metastases. *Int J Radiat Oncol Biol Phys*, 2000. 47(4): p. 1001-6.
4. Nussbaum, E.S., et al., Brain metastases. Histology, multiplicity, surgery, and survival. *Cancer*, 1996. 78(8): p. 1781-8.
5. Sperduto, P.W., et al., Summary report on the graded prognostic assessment: an accurate and facile diagnosis-specific tool to estimate survival for patients with brain metastases. *J Clin Oncol*, 2012. 30(4): p. 419-25.
6. Tsao, M.N., et al., Whole brain radiotherapy for the treatment of newly diagnosed multiple brain metastases. *Cochrane Database Syst Rev*, 2012. 4: p. CD003869.
7. Young, D.F., et al., Rapid-course radiation therapy of cerebral metastases: results and complications. *Cancer*, 1974. 34(4): p. 1069-76.
8. Rades, D., et al., Dose escalation beyond 30 grays in 10 fractions for patients with multiple brain metastases. *Cancer*, 2007. 110(6): p. 1345-50.
9. Chao, J.H., R. Phillips, and J.J. Nickson, Roentgen-ray therapy of cerebral metastases. *Cancer*, 1954. 7(4): p. 682-9.
10. Gaspar, L.E., et al., The role of whole brain radiation therapy in the management of newly diagnosed brain metastases: a systematic review and evidence-based clinical practice guideline. *J Neurooncol*, 2010. 96(1): p. 17-32.

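### Section 5.6 takes patients off study on any Section 5.4 criterion, which contradicts the two-year follow-up in Section 5.5 and can make the censoring of icPFS, OS and late toxicity informative

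*Combined protocol and SAP*

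**What the plan says.** Section 5.4 sets treatment, one week of acute observation and then "6-months from the completion of WBRT for delayed toxicity or until one of the following criteria applies". The list that follows begins with "Disease progression", with no restriction to the brain. It continues with intercurrent illness, unacceptable adverse events, patient withdrawal and a change in condition judged by the investigator.

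Section 5.6 makes that list the rule for leaving the study: "Patients will go off study when any of the criteria listed in Section 5.4 applies".

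Section 5.5 sets a different end of follow-up: "Patients will be evaluated for up to two years from the study registration or until death, whichever occurs first". Its one sentence about patients already removed covers a single route: "Patients removed from study for unacceptable adverse event(s) will be followed until resolution or stabilization of the adverse event". In the Section 10 calendar, footnote k to the Off Study column reads "To be performed only if feasible if the patient is removed from the study".

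On analysis, Section 11.1.6 states "Intracranial PFS will be measured from the date of start of treatment to time of progression or death, whichever occurs first". Section 13.4.4 uses Kaplan-Meier, in which "patients alive without intracranial progression at last follow-up will be censored at the date of the last radiologic assessment"; for OS, patients alive at last follow-up are censored. It has no rule for patients taken off study.

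**The concern.** Progression, illness, toxicity and decline are reasons for removal that may also carry prognostic information. Kaplan-Meier assumes that a censored patient has the same future risk as those still under observation. If patients leave observation because they are doing badly, that assumption fails and the curve is too high.

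Three results are exposed: six-month icPFS, OS, and the six-month late-toxicity assessment. The last also feeds the independent board's review in Section 5.1.3, which is triggered when late toxicity of grade 3 or higher exceeds 20%. Sites also cannot tell from the text whether 5.5 or 5.6 governs.

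**Working it through.** **1. The passages side by side.** The plan states no figure on this point to reproduce.

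| Patient event | Under 5.4 with 5.6 | Under 5.5 | What the endpoint needs |
|---|---|---|---|
| Intracranial progression | off study | followed to two years or death | icPFS event already recorded; OS still needs follow-up |
| Extracranial progression only (literal reading) | off study | followed to two years or death | not an icPFS event; icPFS, late toxicity and OS all need follow-up |
| Intercurrent illness or decline | off study | followed to two years or death | as above |
| Unacceptable adverse event | off study | two years or death, but if removed, followed until the event resolves or stabilizes | as above |

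Elsewhere the plan limits assessment by intracranial progression only: the delayed neurological objective (1.2.5), the neurocognitive and quality-of-life visits (Section 10, footnote j) and Section 13.4.5. A patient who progresses only outside the brain is therefore meant to remain assessable.

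The protocol can separate leaving treatment from leaving the study. Section 6 removes a patient with a DLT from IPdR and still allows WBRT to be completed. Section 5.6 does not make that distinction.

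**2. Size of the icPFS bias (illustration; none of these inputs is in the documents).** Assume constant hazards:
- *a* = icPFS event hazard before removal, from a median of 6 to 8 months: a = ln 2 / median.
- *e* = hazard of the removing event, here extracranial progression, from a cumulative 30% to 50% by six months: e = −ln(1 − proportion)/6.
- *r* = hazard ratio after removal, 1.5 to 3.

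With everyone followed, the true six-month icPFS is

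S = exp(−6A) + e·[exp(−6b) − exp(−6A)]/(A − b), where A = a + e and b = r·a.

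With censoring at removal, Kaplan-Meier tends to exp(−6a).

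*Top of the range* (median 6, 50%, r = 3): a = e = 0.1155, A = 0.2310, b = 0.3466. S = 0.250 + 0.1155 × (0.125 − 0.250)/(−0.1155) = 0.375. The Kaplan-Meier limit is 0.500. The overstatement is 0.125.

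*Bottom of the range* (median 8, 30%, r = 1.5): a = 0.0866, e = 0.0594, A = 0.1461, b = 0.1300. S = 0.572. The Kaplan-Meier limit is 0.595. The overstatement is 0.022.

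*r = 1*: S equals exp(−6a), so the bias is zero.

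Over this grid, e/A × [1 − exp(−6A)] = 22% to 40% of patients are censored at removal by six months. The model censors at the moment of removal. Section 13.4.4 goes back to the last scan, which is not modelled.

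**3. A second parameterisation.** Here the death hazard is calibrated to the 7.1-month median survival that Section 2.1 gives for the best prognostic class. Assumed inputs are a median time to intracranial progression of 12 months, a median time to extracranial progression of 3 to 12 months, and r of 2 to 3 on death. True six-month icPFS is about 0.40 and the Kaplan-Meier limit is 0.43 to 0.52, an overstatement of about 3 to 12 points. For 12-month OS, the smallest gap is 0.363 − 0.289 = 7 points and the largest is 0.545 − 0.261 = 28 points. At r = 1 both are zero.

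**4. Late-toxicity denominator.** Section 5.1.3 plans 16 patients at the RP2D. Taking those as the denominator (an assumption, since the plan does not define it), 3 events give 3/16 = 18.8%, below 20%. If four patients without an event have left, 3/12 = 25%, above 20%. Losing patients who would have had an event moves the figure the other way.

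**The case against.** **The term is undefined.** Section 11.1 evaluates progression under a heading about intracranial metastases. The calendar schedules brain MRI and no extracranial imaging. The plan expects patients to stay under observation through systemic therapy after D35 and extracranial palliative radiotherapy. If progression in 5.4 means intracranial progression, removal at progression does not bias icPFS, because it is already an event. This stands as a limit. A reader might infer that the plan deliberately removes patients at extracranial progression; the documents do not say so, and it is only the literal reading of an unqualified term. Even on the narrow reading, OS follow-up would end at intracranial progression, and removal for illness, toxicity or decline would still cut icPFS short.

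**Some capture continues after removal.** There is adverse-event follow-up (5.5), an off-study visit if feasible (Section 10), and reporting of attributable serious events beyond 30 days (7.3.3, footnote 1). Late-toxicity capture is therefore incomplete, not absent. None of these provisions secures later scans or survival status.

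**The bias is conditional and modest against the noise.** It does not arise if sites follow 5.5. With 19 to 25 patients (13.2), the standard error of a 50% estimate is √(0.25/19) = 11.5 to √(0.25/25) = 10 points before any censoring. The assumed bias is thus at most about one standard error. These outcomes are to be explored descriptively, with no test attached, and OS is not a listed objective. All of this stands and limits the weight of the point.

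**Late neurotoxicity.** A reader might infer that removed patients are the ones most likely to develop it. Nothing in the documents links the removal criteria to late neurotoxicity, and patients who die sooner have less time to show it. Only their loss from the estimate is established.

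**Conclusion.** The contradiction between 5.6 (with 5.4) and 5.5 is in the current text, and no other section resolves it. Its effect is conditional: it requires sites to apply 5.6 and prognosis to be worse after removal. Under those conditions icPFS and OS tend to be overstated. The 2 to 13 point figure for six-month icPFS rests wholly on assumed progression rates and hazard ratios, and should be read as an order of magnitude. For the 20% review, the loss of patients is clear but the direction of error is not.

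The affected endpoints are secondary and descriptive. The DLT endpoint, assessed at D35, is largely unaffected. The text should be corrected, but the point does not undermine the primary objective.

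**What to change.** - Reconcile 5.4, 5.5 and 5.6 so that leaving protocol treatment and leaving the study are distinct. The treatment-stopping criteria themselves are for the sponsor.
- State that meeting a 5.4 criterion does not by itself end the 5.5 follow-up for intracranial status, late toxicity and survival, unless the patient withdraws consent.
- State in 13.4.4 that extracranial progression, new therapy or coming off protocol treatment is not in itself a censoring event for icPFS or OS. The section does not now list any of these as a reason to censor, but neither does it say how off-study patients are handled.

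The cost is protocol wording. The clinic visits, and the phone contacts allowed after six months, are already scheduled in 5.5.

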6. DOSING DELAYS/DOSE MODIFICATIONS

Since treatment for this Phase 1 study includes only 1 cycle of treatment consisting of 4 weeks of IPdR with 15 fractions of concurrent radiation, treatment with IPdR and WBRT will continue as long as there is no DLT as defined above. There will be no dose modifications if a DLT occurs. Patients experiencing a DLT will be removed from IPdR protocol treatment and may complete WBRT when toxicities recover to < Grade 3 as per institutional standard of care.

Patients experiencing non-treatment related toxicities may have IPdR and WBRT held until toxicities resolve to < Grade 3 for up to 14 days and then they may resume IPdR (at the assigned dose level) and WBRT to complete protocol treatment. Patients who are removed from protocol treatment due to non-treatment related toxicities requiring treatment delay of > 14 days are not assessable for determination of the MTD and will be replaced.

7. ADVERSE EVENTS: LIST AND REPORTING REQUIREMENTS

Adverse event (AE) monitoring and reporting is a routine part of every clinical trial. The following list of AEs (Section 7.1) and the characteristics of an observed AE (Section 7.2) will determine whether the event requires expedited reporting via the CTEP Adverse Event Reporting System (CTEP-AERS) **in addition** to routine reporting.

7.1 Comprehensive Adverse Events and Potential Risks List (CAEPR)

7.1.1 CAEPR for IPdR

Comprehensive Adverse Events and Potential Risks list (CAEPR) for IPdR (NSC 726188)

The Comprehensive Adverse Events and Potential Risks list (CAEPR) provides a single list of reported and/or potential adverse events (AE) associated with an agent using a uniform presentation of events by body system. In addition to the comprehensive list, a subset, the Specific Protocol Exceptions to Expedited Reporting (SPEER), appears in a separate column and is identified with bold and italicized text. This subset of AEs (SPEER) is a list of events that are protocol specific exceptions to expedited reporting to NCI (except as noted below). Refer to the 'CTEP, NCI Guidelines: Adverse Event Reporting Requirements'

http://ctep.cancer.gov/protocolDevelopment/electronic_applications/docs/aeguidelines.pdf for further clarification.

NOTE: Report AEs on the SPEER **ONLY IF** they exceed the grade noted in parentheses next to the AE in the SPEER. If this CAEPR is part of a combination protocol using multiple investigational agents and has an AE listed on different SPEERs, use the lower of the grades to determine if expedited reporting is required.

Version 1.2, April 12, 2019¹

Adverse Events with Possible Relationship to IPdR (CTCAE 5.0 Term)	Specific Protocol Exceptions to Expedited Reporting (SPEER)
A Phase 1 safety study of single dose IPdR in 10 subjects resulted in no treatment-related adverse events. ^{2, 3}	

¹This table will be updated as the toxicity profile of the agent is revised. Updates will be distributed to all Principal Investigators at the time of revision. The current version can be obtained by contacting [contact]. Your name, the name of the investigator, the protocol and the agent should be included in the e-mail.

²We expect the safety profile for oral IPdR to vary somewhat from the safety profile of iododeoxyuridine (IUDR), administered via continuous intravenous infusion in conjunction with localized radiation. Since oral IPdR is converted in the body to IUDR, the side effects of oral IPdR therefore may be similar to those adverse events observed in clinical trials of intravenous IUDR. The adverse events observed in IUDR clinical trials include: acute bowel obstruction, acute gastrointestinal hemorrhage, alanine aminotransferase increased, alkaline phosphatase increased, anemia, aspartate aminotransferase, blood bilirubin increased, diarrhea, nausea, neutrophil count decreased, platelet count decreased, and weight loss.

³One early phase 1 single-dose safety clinical trial of IPdR (5-iodo-2-pyrimidinone-2'-deoxyribose) was conducted that treated 10 subjects resulting in no toxicities associated with IPdR. The safety profile may

be revised during and after clinical trials are conducted using repeated dosing.

There is minimal (i.e., 10 subjects in a single-dose study) human data for IPdR to date, however no adverse events were noted in the study. The following toxicities have been observed during pre-clinical animal studies with IPdR:

Ferrets Only

GASTROINTESTINAL DISORDERS - Diarrhea; Nausea; Vomiting

HEPATOBILIARY DISORDERS - Increased liver weights

INVESTIGATIONS - Alkaline phosphatase increased

METABOLISM AND NUTRITION DISORDERS - Anorexia

NERVOUS SYSTEM DISORDERS - Decreased motor activity

RENAL AND URINARY DISORDERS - Decreased kidney weights

REPRODUCTIVE SYSTEM AND BREAST DISORDERS - Decreased uterus weights

RESPIRATORY, THORACIC AND MEDIASTINAL DISORDERS - Bradypnea

Monkeys Only

NERVOUS SYSTEM DISORDERS - Lethargy

Rats Only

BLOOD AND LYMPHATIC SYSTEM DISORDERS - Anemia; Bone marrow (hyperplasia)

INVESTIGATIONS - Decrease alkaline phosphatase; Decreased hematocrit (Hct); Decrease in serum globulin; Decrease in total protein; Decreased RBC; Increased percentage of reticulocytes; Lobular atrophy in mandibular salivary glands; Lymphocyte count decreased

Ferrets, Rats and Mice (events seen in all three species)

GASTROINTESTINAL DISORDERS - Acute bowel obstruction; Acute GI bleed

HEPATOBILIARY DISORDERS - Increased hepatic cytoplasmic vacuolization

INVESTIGATIONS - Alanine aminotransferase increased; Aspartate aminotransferase increased; Weight loss

Note: IPdR in combination with other agents could cause an exacerbation of any adverse event currently known to be caused by the other agent, or the combination may result in events never previously associated with either agent.

7.2 Adverse Event Characteristics

- **CTCAE term (AE description) and grade:** The descriptions and grading scales found in the revised NCI Common Terminology Criteria for Adverse Events (CTCAE) version 5.0 will be utilized for AE reporting. All appropriate treatment areas should have access to a copy of the CTCAE version 5.0. A copy of the CTCAE version 5.0 can be downloaded from the CTEP web site http://ctep.cancer.gov/protocolDevelopment/electronic_applications/ctc.htm.
- **For expedited reporting purposes only:**
 - AEs for the agent that are ***bold and italicized*** in the CAEPR (i.e., those listed in the SPEER column, Section 7.1.1) should be reported through CTEP-AERS only if the grade is above the grade provided in the SPEER.
 - Other AEs for the protocol that do not require expedited reporting are outlined in section 7.3.4.
- **Attribution** of the AE:
 - Definite – The AE is clearly related to the study treatment.

- Probable – The AE is likely related to the study treatment.
- Possible – The AE may be related to the study treatment.
- Unlikely – The AE is doubtfully related to the study treatment.
- Unrelated – The AE is clearly NOT related to the study treatment.

7.3 Expedited Adverse Event Reporting

7.3.1 Expedited AE reporting for this study must use CTEP-AERS (CTEP Adverse Event Reporting System), accessed via the CTEP Web site (<https://eapps-ctep.nci.nih.gov/ctepaers>). The reporting procedures to be followed are presented in the “NCI Guidelines for Investigators: Adverse Event Reporting Requirements for DCTD (CTEP and CIP) and DCP INDs and IDEs” which can be downloaded from the CTEP Web site (http://ctep.cancer.gov/protocolDevelopment/electronic_applications/adverse_events.htm). These requirements are briefly outlined in the tables below (Section 7.3.3).

In the rare occurrence when Internet connectivity is lost, a 24-hour notification is to be made to CTEP by telephone at [contact]. Once Internet connectivity is restored, the 24-hour notification phoned in must be entered electronically into CTEP-AERS by the original submitter at the site.

